# 5 Analysis

### 5.1 Analysis methods

## 5.1.1 Descriptive analysis of baseline characteristics

For baseline characteristics (as defined in 4.5) descriptive statistics will be presented separately for the two treatment groups, i.e. intervention and control, on NH level as well as on resident level. Categorical data are summarized by absolute and relative frequencies. Continuous data are summarized by mean and standard deviation (SD) as well as median, quartiles and/or interquartile range (IQR), as appropriate. The number of available observations or the number of missing observations are reported separately for treatment groups. On resident level, statistical comparisons using Mann-Whitney U-test, Chi²-test or t-test (according to the data type of the characteristics) will be used to identify any imbalances between the two study groups. On NH level, statistical comparisons are not performed due to randomization.

On resident level, responders and non-responders will be compared descriptively regarding care level, age and sex.

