### 2.2 Randomization

A 1:1 cluster-randomization at the level of NHs stratified by study center and region for experimental and control group was carried out using a computer-based code with variable block sizes with length 2 to 4 (to ensure intervention NHs in every region since it has been promised to the NHs) within each stratum. The randomization list was created by a research associate of the Institute for Medical Biometry and Epidemiology of the University Medical Center Hamburg-Eppendorf, who is not directly involved in the implementation of the research project using R version 3.6.2.

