### 2.3 Sample size

To be allocated to trial: 44 NHs (22 per group) including on average n = 100 residents each, resulting in a target sample size of n = 4.400 (2.200 per group) enrolled patients in total.

To be analysed: n = 1760 residents in 22 NHs per group and n = 3520 residents in 44 NHs in total. Full details of sample size calculation can be found in the study protocol [2].

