## 3 Statistical Principles

### 3.1 Confidence intervals and P values

All applicable statistical tests will be two-sided and at a 5% significance level. Analyses of secondary outcomes will be performed without adjustment for multiplicity. All confidence intervals presented will be 95% and two-sided.

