### At resident level:

All analyses relating to the residents of NHs are performed within a framework of multi-level models.

The secondary endpoints 13. – 17., 19. and 25. – 27. are count data. For these endpoints, a mixed Poisson regression model will be calculated with the corresponding number as dependent variable, realized follow-up time as offset, group (intervention vs. control) as fixed effects, the particular baseline measurement as covariate and region NHs and respective NH as nested random intercepts. The treatment effect is presented as IRR with corresponding 95%-CI and p-value. Marginal estimators (numbers per 100 residents per past 12 -months observation period (from t1 to t2)) with corresponding 95%-CI are given per treatment group.

The secondary endpoints 18., 20. - 24., 28. - 29. and 31 are outcome variables with levels 1 = ``yes'' and 0 = ``no'', i.e. binary outcomes. The secondary endpoint place of death (nursing homes vs. others) is also binary.

For binary outcomes, a mixed logistic regression model will be calculated, taking into account the respective binary outcome as dependent variable, group (intervention vs. control) as fixed effect, the particular baseline measurement as covariate and region of NHs and NH as nested random intercept. The treatment effect is presented as odds ratio (OR) with corresponding 95%-CI and p-value. Marginal estimators (proportions of residents at t2) with corresponding 95%-CI are given per treatment group.

The secondary endpoints 11 a. & b. and 12 are continuous and compared between intervention and control group at t2.

A linear mixed model will be calculated including the respective outcome at t2 as dependent variable, group (intervention vs. control) as fixed effects and region of NHs and NH as nested random intercept.

The treatment effect is presented as mean difference with corresponding 95%-CI and p-value. Marginal estimators with corresponding 95%-CI are given per treatment group.

The secondary outcomes 30. and 32 b. are continuous and compared between intervention and control group as change from baseline at t2.

A linear mixed model will be calculated including change from baseline (t2-t0) as dependent variable, group (intervention vs. control) as fixed effects, the respective baseline value (t0) as covariate and region of NHs and NH as nested random intercept.

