### 5.2 Sensitivity analyses

For the primary endpoint analysis, an evaluation with the negative binomial distribution to detect a possible but not expected overdispersion will be performed.

Further, for both primary and key secondary endpoints, per protocol analyses as well as adherence analyses based on NH and resident level will be performed.

Finally, an adjusted analysis is performed taking into account remarkable (p < 0.05) differences at baseline and t1, regarding the following potential confounders:

20

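### Resident-level baseline tests in SAP 5.1.1 ignore the randomisation by nursing home, so their p-values are too small, and they appear to steer covariate selection in the 5.2 adjusted analysis

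*SAP*

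**What the plan says.** Allocation was by home. SAP 2.2 describes "A 1:1 cluster-randomization at the level of NHs stratified by study center and region".

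For baseline characteristics, SAP 5.1.1 states: "On resident level, statistical comparisons using Mann-Whitney U-test", a chi-square test or a t-test, chosen by the type of variable, and that these "will be used to identify any imbalances between the two study groups". It mentions no adjustment for the nursing home. SAP 3.1 sets the level: "All applicable statistical tests will be two-sided and at a 5% significance level".

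SAP 5.2 then plans a further sensitivity analysis: "an adjusted analysis is performed taking into account remarkable (p < 0.05) differences at baseline and t1". The resident-level candidates listed there are age, sex, marital status, care level and professional degree. All five also stand in the resident-level baseline list of SAP 4.5.

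For resident-level outcomes the SAP does allow for clustering. Under the resident-level heading of 5.1.3 it says: "All analyses relating to the residents of NHs are performed within a framework of multi-level models". The models for endpoints 10a and 10b in the same section carry random intercepts for region, home, resident and event.

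**The concern.** Residents of one home share one allocation. If they also resemble each other in age, care level, marital status or education, the difference between arms varies more than a test on independent residents assumes. The test then calls ordinary chance variation between homes significant more often than 5% of the time. The same problem is handled properly for the resident-level outcomes, so the gap is confined to the baseline comparison.

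Two things are at stake. The report may present baseline differences as statistically significant when they are what randomising 44 homes would be expected to produce. And if the same p-values choose the covariates in 5.2, the content of the adjusted model depends partly on false flags.

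**Working it through.** **The SAP's own figures.** SAP 2.3 gives "44 NHs (22 per group) including on average n = 100 residents each": 44 × 100 = 4400 and 22 × 100 = 2200, as stated. The number to be analysed is 1760 per group, so 2 × 1760 = 3520, as stated, and 1760/22 = 80 residents per home. The power calculation behind these figures is left to the protocol and is not needed here.

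**Inputs.**
- Level: 5%, two-sided (SAP 3.1), so z = 1.96.
- Clusters: 22 homes per group (SAP 2.3).
- Residents per home, m: 80 follows from SAP 2.3. The cohort actually tested is DC2, which holds only long-term residents with informed consent (SAP 1.2). Its size is not given, so m = 20 and m = 40 are added as assumptions.
- ICC of the baseline characteristics: not given. Assumed range 0.01 to 0.05.

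**Formulas.** Design effect DE = 1 + (m − 1) × ICC. Real two-sided error of a test that ignores clustering = 2 × (1 − Φ(1.96/√DE)).

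Example, m = 80 and ICC = 0.02: DE = 1 + 79 × 0.02 = 2.58; √DE = 1.606; 1.96/1.606 = 1.220; error = 22.2%.

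| m | ICC 0.01 | ICC 0.02 | ICC 0.05 |
|---|---|---|---|
| 20 | DE 1.19, 7.2% | DE 1.38, 9.5% | DE 1.95, 16.0% |
| 40 | DE 1.39, 9.6% | DE 1.78, 14.2% | DE 2.95, 25.4% |
| 80 | DE 1.79, 14.3% | DE 2.58, 22.2% | DE 4.95, 37.8% |

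**Where the inflation becomes modest.** The real error stays below 10%, that is below twofold, if the ICC is under about 0.005 at m = 80, 0.011 at m = 40 or 0.022 at m = 20.

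**Simulation check** (22 + 22 homes of equal size, 1500 runs per setting). At m = 80 and ICC 0.05, the t-test rejected in 39.1% of runs, Mann-Whitney in 38.2% and chi-square in 36.9%. At m = 20 and ICC 0.01 the rates were 7.3%, 7.4% and 7.8%. All agree with the formula. A t-test on home means, which respects the clustering, rejected in 3.5% to 5.5% over all settings tried (m = 20, 40, 80; ICC 0.01 to 0.10). The simulation ignored the stratification by region, which would lower the inflation if regions differ, and unequal home sizes, which would raise it.

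**Effect on the five covariates of 5.2.** The chance of at least one false flag is 1 − (1 − p)^5, if the five are treated as independent and given the same ICC. At the nominal 5% this is 22.6%. It becomes 31.3% (m = 20, ICC 0.01), 53.5% (m = 40, ICC 0.02) and 90.7% (m = 80, ICC 0.05). These figures are only indicative: the characteristics are unlikely to be independent or to cluster equally.

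**Link from 5.1.1 to 5.2.** Section 5.2 needs a p-value for each resident-level candidate, and the tests in 5.1.1 are the only ones the SAP specifies that would yield it. Section 5.2 does not cite 5.1.1, so the link is an inference.

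**The case against.** The strongest case on the other side concerns scope and size, and much of it stands.

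*Size.* The SAP supplies neither the ICC nor the DC2 cluster size. A reader might infer that imbalances will be flagged several times too often as a matter of course. The document does not support that: with 20 to 40 residents per home and an ICC of 0.01 the inflation is below twofold. What stands without any assumption about size is the direction: any positive ICC makes the p-values too small.

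*Contradiction.* A reader might take the multi-level sentence in 5.1.3 to contradict 5.1.1 outright. It stands under the secondary outcomes and introduces outcome models, whereas 5.1.1 is a separate section on baseline description. The sentence is not a clear contradiction, but for the same reason it does not repair the baseline tests.

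*Selective recruitment.* A reader might fear that significant baseline differences would be read as selective recruitment in an open-label trial. SAP 2.1 calls the trial observer blinded, and the SAP plans no inference about recruitment from these tests.

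*Link to 5.2.* Section 5.2 speaks of baseline and t1, yet SAP 4.5 measures resident characteristics only at t0. It also selects home-level variables by p-value, although 5.1.1 says no home-level comparisons are made. So the source of the p-values in 5.2 is unstated throughout. For the resident-level list, 5.1.1 remains the only candidate.

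*Consequence.* Secondary analyses are exploratory, and the adjusted model is one of several sensitivity analyses. A flagged difference is a real difference in the sample even if it arose by chance between homes, and an unneeded covariate from a list of five has not been shown to bias anything. This limits the weight of the point but does not make the tests valid.

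**Conclusion.** The point holds in a limited form. As written, the resident-level tests in 5.1.1 ignore the unit of randomisation, and their p-values are too small for any positive ICC. Under an assumed ICC of 0.01 to 0.05, the real error of a nominal 5% test is about 7–16% with 20 residents per home, 10–25% with 40 and 14–38% with 80. Only the figure of 80 comes from the SAP, and it may exceed the DC2 cluster size.

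The reach is narrow. Section 5.2 does not itself name the endpoints of the adjusted analysis; the sentence before it concerns the primary and key secondary endpoints. Of these, the primary endpoint and 9e are analysed at home level, so resident-level covariates matter mainly for 10a ii and 10b ii. A reader might infer that the primary result is at risk; it is not, because the model in 5.1.2 uses only group, follow-up time, region and the baseline hospitalisation rate. The point should still be corrected, because the method is wrong as specified and the remedy is cheap.

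**What to change.** In 5.1.1, replace the resident-level tests by one of two options:
- describe imbalance by standardised differences, without tests; or
- compare the arms by mixed models (linear, logistic or ordinal, according to the variable) with the home as random intercept and with region.

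In 5.2, preferably pre-specify all five resident-level covariates for the adjusted analysis of resident-level endpoints and drop the p < 0.05 selection for them. This is better than merely correcting the tests: a cluster-adjusted test flags fewer differences, so selection by its p-value could leave a prognostic imbalance unadjusted. If selection by p-value is kept, state that only cluster-adjusted p-values are used and from which comparison they come. The same edit should settle the reference to t1, since resident characteristics are measured only at t0, and reconcile the home-level selection in 5.2 with the statement in 5.1.1 that no home-level comparisons are made.

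The cost is SAP wording and, under the second option, a few extra models. No new data are needed.

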### 5.1.2 Primary Outcome

The primary analysis is performed in the ITT population at NH level. For rate comparison a Poisson regression model is calculated taking into account group (intervention vs control) as independent variable, realized follow-up time as offset, region of NHs and the respective baseline hospitalization rate as covariates. The treatment effect is presented as incidence rate ratio (IRR) with corresponding 95%-Confidence interval (CI) and p-value. Marginal estimators (numbers per 100 residents per past 12 -months observation period (from t1 to t2)) with corresponding 95%-CI are given per treatment group.

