### 1.2.2 Secondary Outcomes

The secondary outcomes are as follows, analyzed at t2:

At NH level (DC1):

- 1. number of hospital days (long-term) per 100 residents per past 12 months
- 2. number of hospital stays (long-term) per 100 residents during observation period (without consideration of occupied bed days)
- 3. number of patients with at least one hospitalization per 100 residents per past 12 months
- 4. number of residents who died in the hospital per 100 residents per past 12 months
- 5. number of pre-specified unwanted invasive treatments per 100 residents measured:
  - a. number of residents with feeding tube (PEG) in place (cross-sectional)
  - b. number of residents with PEG in use (cross-sectional)
  - c. number of attempts of cardiopulmonary resuscitation (CPR) per past 12 months
  - d. number of attempts of successful CPR per past 12 months
- 6. number of legal guardians per 100 residents (cross-sectional)
- 7. number of durable powers of attorney (DPOA) per 100 residents (cross-sectional)
- 8. advance directives (ADs)
  - a. number of all advance directives per 100 residents (cross-sectional)
  - b. number of advance directives signed by resident per 100 ADs (cross-sectional)
  - c. number of advance directives last signed in the last 6m per 100 ADs (cross-sectional)
  - d. number of advance directives in long-term care only per 100 ADs (cross-sectional)

- 9. physician or patient/proxy orders for life sustaining treatment in emergencies (POLST-E)
  - a. number of POLST-E per 100 residents (cross-sectional)
  - b. number of POLST-E not signed by resident per 100 POLST-E (cross-sectional)
  - c. number of POLST-E in the last 6m per 100 POLST-E (cross-sectional)
  - d. number of POLST-E with a do-not-hospitalize order per 100 POLST-E (cross-sectional)
  - e. number of POLST-E per 100 residents (long-term care only; cross-sectional)

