### At NH level:

All secondary endpoints are count data.

For the endpoints 1,2, 4 and 5 c. & d., a Poisson Regression model is calculated with the respective number per 100 residents per past 12 months' observation period (from t1 to t2) as dependent variable, group (intervention vs control) as independent variable, number of occupied bed days as offset and the respective baseline rate and region of NHs as covariates.

The treatment effect is presented as incidence rate ratio (IRR) with corresponding 95%-CI and p-value. Marginal estimators (numbers per 100 residents per past 12 -months observation period (from t1 to t2)) with corresponding 95%-CI are given per treatment group.

For the secondary endpoint 3, the number of residents during the observation period before t2 is used as offset variable. The resulting marginal estimators are numbers per 100 residents.

The secondary endpoints 5 a. & b. and 6-7, 8 a. and 9 a. are measured cross-sectional. For these endpoints, a Poisson Regression model is calculated with the respective number as dependent variable, group (intervention vs. control) as independent variable, number of residents as offset and the respective baseline rate and region of NHs as covariates.

The treatment effect is presented as IRR with corresponding 95%-CI and p-value. Marginal estimators (numbers per 100 residents per past 12 -months observation period (from t1 to t2)) with corresponding 95%-CI are given per treatment group.

The secondary endpoints 8 b. - d. and 9 b. - e. are measured cross-sectional, too, but refer to a predefined subgroup.

For these endpoints, a Poisson Regression model is calculated with the respective number as dependent variable, group (intervention vs control) as independent variable and the respective baseline rate and region of NHs as covariates.

For the endpoints 8 b. - d. the number of ADs and for the endpoints 9 b. - e. the number of POLST-Es are set as offset, respectively.

The treatment effect is presented as IRR with corresponding 95%-CI and p-value. Marginal estimators (number per 100 ADs or 100 POLST-Es per past 12 -months observation period (from t1 to t2)) with corresponding 95%-CI are given per treatment group.

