### 5.4.3 Possible pre-defined analyses not to be presented in the study report

All secondary endpoints may be analysed as defined in the different sensitivity or adjusted analyses, as well as regarding the pre-defined subgroups and the possible impact of the Covid-19 pandemic, if it is of interest.

Furthermore, sensitivity and subgroup analyses of the other (not key) secondary outcomes might be performed.

These analyses are pre-defined but will not be part of the study report.

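### The confirmatory Poisson model makes no allowance for extra-Poisson variation between nursing homes, and no rule lets the negative binomial replace it

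*SAP*

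**What the plan says.** Section 1.2 states that each home supplies pooled data on its residents (DC1). Section 5.1.2 analyses the primary outcome at nursing-home level, so the model has one count per home. The specification reads "For rate comparison a Poisson regression model is calculated taking into account group (intervention vs control) as independent variable, realized follow-up time as offset", followed by "region of NHs and the respective baseline hospitalization rate as covariates". The incidence rate ratio, 95% CI and p-value from this model are the confirmatory result. Section 3.1 fixes the level: "All applicable statistical tests will be two-sided and at a 5% significance level".

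Overdispersion is mentioned once, among the sensitivity analyses in 5.2: "an evaluation with the negative binomial distribution to detect a possible but not expected overdispersion will be performed". No criterion for detecting it is given, and nothing says what happens to the primary result if it is found.

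The nursing-home-level secondary counts in 5.1.3 use the same model: "For the endpoints 1,2, 4 and 5 c. & d., a Poisson Regression model is calculated". Endpoint 1 is the "number of hospital days (long-term) per 100 residents per past 12 months". For secondary endpoints, sensitivity analyses are optional under 5.4.3, which adds: "These analyses are pre-defined but will not be part of the study report".

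**The concern.** A Poisson model with model-based standard errors is valid only if, after adjustment, the counts vary no more than Poisson counts do. Two features of this outcome work against that.

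- **Homes differ.** Region and the observed baseline rate absorb part of the difference but not all of it. The observed baseline rate measures a home's underlying rate with error, and that underlying rate can change between baseline and follow-up.
- **Stays repeat.** The numerator in 1.2.1 is all hospitalisations, so several stays of one resident count separately although they are not independent.

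Whatever variation remains goes into the count but not into the standard error. The single confirmatory test would then reject too often under the null, and about half of those rejections would favour the programme. If overdispersion is detected, the plan either leaves the Poisson p-value standing or leaves the team to choose between two results after seeing both.

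**Working it through.** **Inputs from the SAP**
- 44 homes, 22 per group (2.3), in 8 regions (2.1: four centres with two regions each).
- Size per home from "n = 3520 residents in 44 NHs in total": 3520 / 44 = 80, taken as 80 resident-years over the 12-month observation period.
- Two-sided 5% level (3.1).

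**Assumed inputs, because the SAP gives none**
- 30, 60 or 100 hospitalisations per 100 residents per year, so the expected count per home is m = 80 × 0.3 = 24, 80 × 0.6 = 48 or 80 × 1.0 = 80.
- Between-home CV from 0 to 0.30.
- Correlation of home effects between baseline and follow-up of 0, 0.5 or 0.8.

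The SAP has no figure of its own to reproduce here, since 2.3 refers the sample-size calculation to the protocol.

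**Step 1: formula.** With residual between-home CV k, the variance of a home's count is m(1 + m·k²). The Poisson standard error is too small by √φ, where φ = 1 + m·k². The real two-sided level is 2[1 − Φ(1.96/√φ)]. Example with m = 80 and k = 0.10: φ = 1 + 80 × 0.01 = 1.80, √φ = 1.34, 1.96/1.34 = 1.46, level 14.4%.

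**Step 2: simulation of the planned model.** 5000 null trials per setting: 44 homes, 5-6 per region, balanced within region; mean 80 resident-years per home (CV 0.3); log-normal home effects; region SD 0.1 on the log scale. The Poisson model contains group, seven region indicators, baseline rate and a log resident-years offset. The CV here is the total before adjustment; in the formula it is the residual.

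| CV | φ (m = 24, 48, 80) | Level by formula | Simulated level, planned model | Of which favouring the programme (nominal 2.5%) |
|---|---|---|---|---|
| 0 | 1 | 5.0% | 4.9-5.2% | 2.3-2.6% |
| 0.05 | 1.06, 1.12, 1.20 | 5.7-7.4% | 5.4-7.6% | 2.6-4.0% |
| 0.10 | 1.24, 1.48, 1.80 | 7.8-14.4% | 7.5-14% | 3.7-6.8% |
| 0.20 | 1.96, 2.92, 4.20 | 16-34% | 14-35% | 7-17% |
| 0.30 | 3.16, 5.32, 8.20 | 27-49% | 21-50% | 10-25% |

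**Step 3: does baseline adjustment remove the problem?** In a second set-up (2000 null trials per setting, 40 or 80 hospitalisations per 100 residents per year), homes differed persistently with an assumed log-scale SD of 0.3 and log baseline rate was a covariate. With no new between-home variation after baseline, the Poisson level was still 14-16%, because the observed baseline rate carries sampling error. With a residual CV of 0.10 added, it was 17-22%.

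**Step 4: repeat admissions alone.** Set the between-home CV to 0 and let each stay be followed by another with assumed probability p. Then φ = (1 + p)/(1 − p).
- p = 0.10: φ = 1.1/0.9 = 1.22, level 7-8%.
- p = 0.20: φ = 1.2/0.8 = 1.50, level 11%.
- p = 0.30: φ = 1.3/0.7 = 1.86, level 15-16%.

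**Step 5: variance-corrected model.** Same terms, Pearson scale with a floor of 1, t reference. Parameters: intercept, group, seven regions, baseline rate = 10, so 44 − 10 = 34 degrees of freedom. In the step 2 trials the level was 3.3-3.6% at CV 0, 3.6-5.4% at CV 0.05-0.10 and 4.8-6.8% at CV 0.20-0.30.

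**Step 6: hospital days (endpoint 1).** The variance factor is E[L²]/E[L] for length of stay L. For an assumed constant stay of 5 or 10 days it equals 5 or 10, so the Poisson standard error is √5 = 2.2 to √10 = 3.2 times too small, before any difference between homes.

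**The case against.** The strongest reply is that the SAP already deals with overdispersion. It names the issue and pre-specifies a negative binomial analysis of the primary endpoint. That analysis is not among those which 5.4.3 keeps out of the report, so readers would see both results. The Covid-19 model in 5.4.2 also puts a random intercept for home on the primary outcome. All this is true, and it would make a problem visible. It does not change which result is confirmatory: 5.2 is a sensitivity analysis without a governing rule, and 5.4.2 serves another purpose.

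Second, the size rests on assumed inputs, and nothing in the SAP places this trial between no inflation and a level near 50%. The grounds for not expecting overdispersion may lie in the protocol or in the pooled baseline analyses. That stands, and the figures are illustrative. The direction does not depend on them: any positive residual variation makes the interval too narrow.

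Third, quasi-Poisson is not the only valid remedy, and its floor of 1 is optional. This also stands. In a separate run of 3000 trials per setting at CV 0, dropping the floor gave a level of 4.1-5.0% instead of 2.8-3.7%, and power of 73-75% instead of 69-73% (plain Poisson 75-78%). Roughly half of the power cost therefore comes from the floor.

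Finally, the secondary counts are exploratory and carry no confirmatory error rate, so they are a side point.

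**Conclusion.** The concern holds and must be fixed, because it affects the only confirmatory test. As written, 5.1.2 assumes no extra-Poisson variation, and 5.2 provides no route for another model to take over. If there is no overdispersion, the planned model keeps its 5% level. If there is, the level is exceeded: on the assumed ranges, modestly at a between-home CV of 0.05, up to about 14% at 0.10 and up to about 35% at 0.20. Covariate adjustment did not remove this in either simulation set-up. Since the SAP gives no figure showing which case applies, the validity of the primary test should not depend on it.

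**What to change.** In 5.1.2, make the primary model a quasi-Poisson regression with the same terms, Pearson scale not below 1, and a t reference on the residual degrees of freedom (34 with 44 homes and 8 regions). In 5.2, keep plain Poisson and negative binomial as sensitivity analyses. Apply the same variance correction to the nursing-home-level count models in 5.1.3, above all endpoint 1. Another standard variance correction, or a governing rule fixed before unblinding, would also close the main gap; a rule is the weaker choice.

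This needs no new data and about one sentence each in 5.1.2 and 5.2. The statistical price falls where there is no overdispersion: the test is then slightly conservative (3.3-3.6%), and simulated power drops from 76-77% to 70-72% for rate ratios of 0.839, 0.883 and 0.908 at 30, 60 and 100 hospitalisations per 100 residents per year. Omitting the floor recovers about half of that loss. With overdispersion the interval is wider but close to its stated level. The effect on planned power cannot be judged from the SAP, because the sample-size basis is in the protocol.
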